11.2.3 Medical history

Relevant medical history from the subject's birth must be recorded.

- Skin disease history: all past and current skin disease history including:
 - Alopecia.
 - Vitiligo.
 - Herpes simplex.
- Atopy history:
 - Onset of AD disease.
 - Previous treatments for AD.
 - Asthma.
 - Food allergy.
 - Hay fever.

- Allergic conjunctivitis.
 - Atopic keratoconjunctivitis.
 - Cataract.
 - Glaucoma.
 - Eczema herpeticum.
- Other medical and surgical history including concurrent diagnoses within the previous 12 months. For each condition, diagnosis or surgical procedure, the start date and stop date or whether it is ongoing will be recorded.

11.2.4 Height and weight

The subject's height (without shoes) will be measured; the subject's weight (in indoor clothing and without shoes) will be measured.

11.2.5 Body surface area involvement

The total BSA affected by AD will be assessed by the investigator for each section of the body component A of SCORAD (see Section 11.3.3) and will be reported as a percentage of all major body sections combined. The following body regions will be assessed (with the highest possible score for each region in brackets): head and neck (9%), anterior trunk (18%), back (18%), upper limbs (18%), lower limbs (36%) and genitals (1%).

The total BSA score will be assessed according to the schedule of procedures ([Panel 2](#)).

11.3 Efficacy assessments

11.3.1 Eczema Area and Severity Index (EASI)

The EASI is a validated measure used in clinical practice and clinical trials to assess the severity and extent of AD ([Hanifin et al. 2001](#), [Tofte et al. 1998](#)). The EASI score will be assessed according to the schedule of trial procedures (Section 4). The assessment will be based on the condition of the disease at the time of evaluation and not in relation to the condition at a previous visit.

The EASI is a composite index with scores ranging from 0 to 72, with higher values indicating more severe or more extensive condition. The index will be calculated as shown in [Panel 8](#). Briefly, the investigator will assess the severity of 4 AD disease characteristics (erythema, induration/papulation, excoriation, and lichenification) on the 4 body regions (head/neck, trunk, upper extremities, lower extremities); severity will be assessed according

to the scale shown in Panel 9. For each body region, a severity sum score will be calculated which will be multiplied by an area score (Panel 9) and by a weighting factor. The EASI score equals the sum of the scores obtained for each body region (Panel 8). The EASI score will be calculated automatically.

Panel 8: Calculation of the Eczema Area and Severity Index

Body region	Erythema	Induration/ papulation	Excoriation	Lichenification	Area score	Weighting factor	Score
Head/neck	(SS +	SS +	SS +	SS)	x AS	x 0.1	
Trunk	(SS +	SS +	SS +	SS)	x AS	x 0.3	
Upper extremities	(SS +	SS +	SS +	SS)	x AS	x 0.2	
Lower extremities	(SS +	SS +	SS +	SS)	x AS	x 0.4	
The EASI score is the sum of the 4 body region scores							  (range 0–72)

AS, area score; EASI, Eczema Area and Severity Index; SS, severity score. Modified from (HOME website).

Panel 9: EASI severity score scale and area score scale

Severity score scale	
0	None/absent
1	Mild
2	Moderate
3	Severe

Note: half-steps (0.5, 1.5, 2.5) are allowed.

Area score scale	
0	0% affected area
1	1% to 9% affected area
2	10% to 29% affected area
3	30% to 49% affected area
4	50% to 69% affected area
5	70% to 89% affected area
6	90% to 100% affected area

EASI, Eczema Area and Severity Index

11.3.2 Validated Investigator Global Assessment scale for Atopic Dermatitis (vIGA-AD)

The vIGA-AD is an instrument used in clinical trials to assess the subject's global disease severity and is based on a 5-point scale ranging from 0 (clear) to 4 (severe) (Panel 10). The vIGA-AD score will be assessed at time points according to the schedule of trial procedures (Section 4). The assessment will be based on the condition of the disease at the time of evaluation and not in relation to the condition at a previous visit. New lesions that occurred on previously untreated areas will be included in the assessment.

The vIGA-AD score is selected using the descriptors in Panel 10 that best describe the overall appearance of the lesions at a given time point. It is not necessary that all characteristics under morphological description be present.

Panel 10: Validated Investigator Global Assessment scale for Atopic Dermatitis

Score	Morphological description
0 - Clear	No inflammatory signs of atopic dermatitis (no erythema, no induration/papulation, no lichenification, no oozing/crusting). Post-inflammatory hyperpigmentation and/or hypopigmentation may be present.
1 - Almost clear	Barely perceptible erythema, and barely perceptible induration/papulation, and/or minimal lichenification. No oozing or crusting.
2 - Mild	Slight but definite erythema (pink), slight but definite induration/papulation, and/or slight but definite lichenification. No oozing or crusting.
3 - Moderate	Clearly perceptible erythema (dull red), clearly perceptible induration/papulation, and/or clearly perceptible lichenification. Oozing and crusting may be present.
4 - Severe	Marked erythema (deep or bright red), marked induration/papulation, and/or marked lichenification. Disease is widespread in extent. Oozing or crusting may be present.

Reference: [Eli Lilly and Company 2017](#)

11.3.3 Scoring Atopic Dermatitis (SCORAD)

The SCORAD is a validated tool to evaluate the extent and severity of AD lesions, along with subjective symptoms ([European Task Force on Atopic Dermatitis 1993](#)). The maximum total score is 103, with higher values indicating more severe disease. SCORAD will be assessed according to the schedule of trial procedures (Section 4).

The assessment will be based on the condition of the disease at the time of evaluation and not in relation to the condition at a previous visit. Whenever possible, SCORAD should be assessed by the same investigator at each visit to reduce inter-rater variability.

The assessment consists of 3 components: A = extent, B = intensity, and C = subjective symptoms.

Extent (A)

The extent of AD is assessed as a percentage of each defined body area and reported as the sum of all areas (maximum score = 100%).

Intensity (B)

The intensity of 6 specific symptoms of AD (erythema, edema/papulation, oozing/crusting, excoriation, lichenification, and dryness) is assessed by the investigator on an average representative area using the following scale:

- | | | |
|---|---|-------------|
| 0 | = | None/absent |
| 1 | = | Mild |
| 2 | = | Moderate |
| 3 | = | Severe |

Note: dryness is evaluated on uninvolved areas.

The sum of intensity score of the 6 symptoms will be reported (maximum score = 18).

Subjective symptoms (C)

A subjective assessment of the average itch and sleeplessness over the last 3 days/nights is recorded for each symptom by the subject on a visual analogue scale, where 0 is no itching (or no trouble sleeping) and 10 is unbearable itching (a lot of trouble sleeping), with a maximum possible score of 20. The subjective assessment will be completed by the subjects together with the PROs using the electronic device.

The SCORAD is calculated as: $A/5+7B/2+C$. The SCORAD will be calculated automatically.

11.4 Safety assessments

11.4.1 Vital signs

Vital signs (resting blood pressure, pulse, and body temperature) will be assessed according to the schedule of trial procedures (Section 4). Vital signs will be measured in a supine position following at least 5 minutes of rest.

If an abnormal vital sign at screening is considered to be clinically significant by the investigator, it will be at the discretion of the investigator if the subject should be randomised into the trial (respecting exclusion criterion no. 20).

In case of abnormal findings, the vital sign measurement can be repeated approximately 15 minutes later with subjects resting in a supine position to verify the first measurement. Should the repeated measurement result in a normal value, the measurement must be repeated once more. If the third measurement verifies the second (normal) value, the first measurement should be considered false. If the third measurement confirms the first measurement (abnormal), the second measurement will be considered false. Only the last value measured and considered correct will be recorded in the eCRF.

Reporting in eCRF

Vital signs will be recorded in the eCRF. Clinically significant abnormal vital signs at the screening visit will be documented as medical history in the eCRF. At subsequent visits, any clinically significant deterioration of a pre-existing condition as well as any new clinically significant sign, symptom or illness will be reported as an AE in accordance with Section 13.3.

11.4.2 Physical examination

A thorough physical examination of the subject including whole body inspection of the skin and auscultation of heart, lungs and abdomen; palpitation of the abdominal organs and basic neurological status must be performed according to the schedule of trial procedures (Section 4). The investigator should perform the same examinations as in clinical practice as a minimum.

If the screening physical examination results in a finding, which is abnormal and of clinical significance, it will be at the investigator's discretion to decide if the subject should be randomised into the trial (respecting exclusion criterion no. 20).

Reporting in eCRF

It will be recorded in the eCRF if a physical examination was performed and the investigator's evaluation ('normal', 'abnormal, not clinically significant', 'abnormal, clinically significant'); if a physical examination was not performed, a reason must be given.

Clinically significant abnormal findings at the screening visit will be documented as medical history in the eCRF. At subsequent visits, any clinically significant deterioration of a pre-existing condition as well as any new clinically significant sign, symptom or illness will be reported as an AE in accordance with Section 13.3.

11.4.3 ECG

A single 12-lead resting digital ECG will be recorded after the subject has been supine for at least 5 minutes at the visits indicated in the schedule of trial procedures (Section 4).

A preliminary evaluation of the ECGs will be performed by the investigators to evaluate immediate subject safety. As a minimum, the date of ECG collection will be recorded in the source documents.

The ECG data will be transferred to a central ECG service company for central evaluation. A cardiologist at the ECG service company will analyse and interpret the ECG data. The ECG service company will provide ECG evaluation reports to the trial sites.

The investigator must evaluate all abnormal ECG results ('clinically significant' or 'not clinically significant') and sign and date. The investigator has the final decision on the clinical significance of ECG abnormalities.

If the screening ECG results in a finding, which is abnormal and of clinical significance, it will be at the investigator's discretion to decide if the subject should be randomised into the trial (respecting exclusion criterion no. 20).

The collection and transmission of ECG data will be described in a separate ECG manual. Test dummy transmissions will be undertaken prior to the trial conduct to ensure that transmissions can be made, and that date and time settings are correctly set.

Reporting in eCRF

It will be recorded in the eCRF if an ECG was performed and the investigator's assessment of ECG results ('normal', 'abnormal, not clinically significant', 'abnormal, clinically significant'); if an ECG was not performed, a reason must be given.

Clinically significant abnormal findings at the screening visit will be documented as medical history in the eCRF. At subsequent visits, any clinically significant deterioration of a pre-existing condition as well as any new clinically significant sign, symptom or illness will be reported as an AE in accordance with Section 13.3.

11.4.4 Laboratory testing

Blood and urine samples will be collected according to the schedule of trial procedures (Section 4). See Panel 11 for an overview of the individual clinical laboratory parameters to be assessed in this trial.

Central laboratory

Chemistry, haematology, urinalysis (if applicable), serology, and serum pregnancy tests will be analysed by a central laboratory which will provide results to the trial sites. The investigator must evaluate all results outside the reference range ('clinically significant' or 'not clinically significant') and sign and date. The signed and dated version will be filed with the investigator's trial documentation. Clinically significant abnormal tests must be repeated to confirm the abnormality.

If a screening laboratory result is abnormal and of clinical significance, it will be at the investigator's discretion to decide if the subject should be randomised into the trial (respecting exclusion criteria no. 16, 20, 21, 22, and 29).

A laboratory manual will be provided to the trial sites specifying the procedures for collection, processing, storage, and shipment of samples, as well as laboratory contact information specific to this trial.

Tests performed at the trial site

Urine samples will be tested at the trial site with a dipstick; if abnormal, a urine sample will be sent to the central laboratory for further analysis.

Women of childbearing potential will have a urine pregnancy test performed at the trial site at visits indicated in the schedule of trial procedures in Section 4.

Panel 11: Clinical laboratory tests

Chemistry	Haematology
Sodium	Erythrocytes
Potassium	Haematocrit
Creatinine	Haemoglobin
Urea nitrogen	Erythrocyte mean corpuscular volume
Calcium	Erythrocyte mean corpuscular haemoglobin concentration
Alkaline phosphatase	Leukocytes
Aspartate aminotransferase	Neutrophils, neutrophils/total cells
Alanine aminotransferase	Lymphocytes, lymphocytes/total cells
Gamma glutamyl transferase	Monocytes, monocytes/total cells
Bilirubin ^a	Eosinophils, eosinophils/total cells
Lactate dehydrogenase	Basophils, basophils/total cells
Cholesterol	Thrombocytes
LDL cholesterol	Serology^b
HDL cholesterol	Hepatitis B virus surface antigen
Triglycerides	Hepatitis B virus surface antibody
Glucose (non-fasting)	Hepatitis B virus core antibody
Albumin	Hepatitis C virus antibody
Protein	HIV-1 antibody
C-reactive protein	HIV-2 antibody
	Immunoglobulin E
	Tuberculosis test^{b,c}
	Interferon gamma release test
Urinalysis^d	Serum pregnancy test^{b,e}
Protein	Choriogonadotropin beta
Glucose	
Ketones	
Occult blood	
Leukocytes	
Nitrite	

- a) If bilirubin is above ULN, direct and indirect bilirubin will also be measured.
- b) Measured at screening only
- c) Subjects with high risk of latent tuberculosis (e.g. prior residence in or travel to countries with high prevalence of tuberculosis, close contact with a person with active tuberculosis, or a history of active or latent tuberculosis where an adequate course of treatment cannot be confirmed) must be tested.
- d) Urine samples will be tested at the trial site (dipstick). In case of abnormal dipstick results, a urine sample will be sent to the central laboratory for microscopic examination (leukocytes, erythrocytes, and casts)
- e) Only female subjects of childbearing potential. In addition, urine pregnancy tests will be performed at the trial site.

Abbreviations: HDL, high density lipoprotein; HIV: human immunodeficiency virus; LDL, low density lipoprotein.

Reporting in eCRF

The site staff will record in the eCRF if a sample was taken and the investigator's assessment of the results ('normal', 'abnormal, not clinically significant', 'abnormal, clinically significant').

The date and the outcome of the urine pregnancy test will be recorded in the eCRF ('positive', 'negative').

Clinically significant abnormal laboratory results at the screening visit will be documented as medical history in the eCRF. At subsequent visits, any clinically significant deterioration of a pre-existing condition as well as any new clinically significant sign, symptom or illness will be reported as an AE in accordance with Section 13.3.

11.4.5 Subject assessment of local tolerability

Subjects will provide an assessment of local tolerability according to the schedule of trial procedures (Section 4).

The subject will retrospectively be asked by the investigator to assess stinging/burning in connection with the IMP applications since their last visit. The highest (worst) skin reaction score across treatment area(s) will be recorded in the eCRF by use of the 4-point scale shown in Panel 12.

Panel 12: Subject assessment of local tolerability after IMP application

Grade	Stinging/burning
0 (none)	No stinging or burning
1 (mild)	Slight warm, tingling sensation, not really bothersome
2 (moderate)	Definitive warm, tingling sensation, that is somewhat bothersome
3 (severe)	Hot, tingling/stinging sensation that has caused definite discomfort

Subject assessment of local tolerability will be performed after safety assessments by the investigator (Panel 6). Local tolerability reactions are not reported as AEs; however, if they qualify as an SAE, they will be reported as described in Section 13.4.1.

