10.1 General principles

A subject may withdraw from the trial (i.e. withdraw from treatment and protocol-defined interventions) or permanently discontinue trial treatment (i.e. stop treatment only but agree to continued protocol-defined interventions) at any time (prior to first dose or during the treatment period) if the subject, the investigator, or LEO considers that it is not in the subject's best interest to continue.

If a subject withdraws from the trial, he/she may request destruction of any samples taken and not tested, and the investigator must document this in the subject's source documentation.

Subjects who withdraw from the trial and subjects who discontinue trial treatment will not be replaced.

Data to be recorded in the eCRF

The primary reason for withdrawal from the trial and discontinuation of IMP must be recorded in the medical records and on the end of trial form in the eCRF where the following options are available:

- Lack of efficacy.
- Adverse event.
- Withdrawal by subject.
- Lost to follow-up.
- Pregnancy.
- Death.
- Other.

If 'adverse event' or 'other' is selected, a specification must be provided in the eCRF with a clear link to the specific AE if applicable.

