13.3 Reporting of adverse events

AEs reported by the subject or observed by the investigator must be recorded on the AE form of the eCRF and should be described in the following manner:

The *AE term* must be in precise English medical terminology (that is, not necessarily the exact words used by the subject). Whenever possible, a specific diagnosis should be stated (for example ‘allergic contact dermatitis’).

For cutaneous AEs, the *location* must be part of the AE description and may be described as [e.g. the face, scalp, back, chest, arm, leg, trunk or limb]. Additionally, the location should be described using the following terminology:

- Lesional/perilesional (≤ 2 cm from the border of lesion(s) treated with IMP).
- Distant (>2 cm from the lesion border).

The *duration* of the AE must be reported by the start date and stop date of the event (it will also be recorded if the event is ongoing). In addition, it will be recorded if the AE started prior to start of IMP.

AEs must be classified in terms of severity, causality and outcome according to the definitions in [Appendix 2](#).

Action taken with IMP: any action taken with IMP as a consequence of the AE must be recorded (dose not changed, drug withdrawn, not applicable, unknown).

Other action taken: any other action taken as a result of the AE must be recorded (none, concomitant medication, concurrent procedure).

Withdrawn from trial due to this AE: it must be recorded whether the AE led to withdrawal from the trial.

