14.3.9.1 Adverse events

AEs will be coded during the course of the trial according to MedDRA. AEs will be presented by preferred terms and primary SOC.

Treatment-emergent AEs will be summarised; however, all AEs recorded during the course of the trial will be included in subject data listings. An event will be considered treatment-emergent if started after the first use of IMP or if started before the first use of IMP and worsened in severity after first dose of IMP. The tabulations described in the following will only include the treatment-emergent events. In each of the tabulations, AEs are defined by MedDRA preferred terms within primary SOC.

An overall summary of the number of events and the number (percentage) of subjects with any treatment-emergent AEs, deaths, SAEs, premature discontinuations from the trial due to AEs, treatment-related AEs and severe AEs will be presented.

The number of AEs and number of subjects with each type of AEs will be tabulated by treatment group.

The severity for each type of AE will be tabulated by treatment group. Where there are several recordings of severity for a given type of AE, severity will be taken as the most severe recording for that AE.

The causal relationship to IMP for each type of AE will be tabulated by treatment group. Where there are several recordings of causal relationship to the IMP for a given type of AE, causal relationship will be taken as the most-related recording from the last report of that AE, since that is when the investigator will be in possession of most information and therefore be best able to judge causal relationship.

Related AEs are defined as AEs for which the investigator has not described the causal relationship to IMP as 'not related'. The number of subjects with each type of related AE will be tabulated.

SAEs will be evaluated separately and a narrative for each will be given.

Adverse events of special interest will be tabulated by treatment group and listed.

AEs leading to withdrawal from trial and AEs leading to permanent discontinuation of IMP will be tabulated by treatment group and listed.

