14.3.9.4 Subject assessment of local tolerability

Subject assessment of local tolerability will be summarised by visit and treatment group.

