Appendix 1: Definitions of adverse events and serious adverse events

Adverse event definition

An AE is defined as any untoward medical occurrence in a patient or clinical investigation subject administered a pharmaceutical product and which does not necessarily have a causal relationship with this treatment. An AE can therefore be any unfavourable and unintended sign (including an abnormal laboratory finding), symptom, or disease temporally associated with the use of a medicinal (investigational) product, whether or not related to the medicinal (investigational) product. (ICH GCP Guideline)

This definition includes:

- Accidental injuries.
- Events related to trial procedures.
- Reasons for any unfavourable and unplanned change in medication (drug and/or dose).
- Clinically significant worsening of pre-existing conditions.
- Reasons for admission to hospital or surgical procedures unless these were planned before the subject consented to trial participation.
- AEs commonly observed and AEs anticipated based on the pharmacological effect of the IMP.
- Any laboratory abnormality assessed as clinically significant by the investigator (see Section 11.4.4).

Serious adverse event definition

An SAE is any untoward medical occurrence that

- Results in death.
- Is life-threatening.
- Requires inpatient hospitalisation or prolongation of existing hospitalisation. Planned hospitalisation or planned prolonged hospitalisation do not fulfil the criteria for being an SAE but should be documented in the subject's medical record.

- Results in persistent or significant disability/incapacity.
- Is a congenital anomaly/birth defect.

or

- Is a medically important condition. Events that may not be immediately life-threatening or result in death or hospitalisation but may jeopardise the subject or may require intervention to prevent one of the other outcomes listed in the definition above. Examples are intensive treatment in an emergency room or at home for allergic bronchospasm, blood dyscrasias and convulsions that do not result in hospitalisation, development of drug dependency or drug abuse

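### Section 11.4.5 keeps non-serious stinging/burning off the AE form, contrary to Appendix 1, so a reaction that ends IMP use can be missing from the AE tables

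*Combined protocol and SAP*

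**What the plan says.** Section 11.4.5 has the investigator ask the subject about stinging/burning since the last visit, graded 0 to 3. "The highest (worst) skin reaction score across treatment area(s) will be recorded in the eCRF". The section then sets the reporting rule: "Local tolerability reactions are not reported as AEs; however, if they qualify as an SAE, they will be reported as described in Section 13.4.1". Section 14.3.9.4 plans one output: "Subject assessment of local tolerability will be summarised by visit and treatment group".

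The general AE rules read differently. Appendix 1 lists among AEs "Reasons for any unfavourable and unplanned change in medication (drug and/or dose" and "AEs commonly observed and AEs anticipated based on the pharmacological effect of the IMP". Section 13.3 states: "AEs reported by the subject or observed by the investigator must be recorded on the AE form of the eCRF". Neither place exempts stinging or burning.

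For discontinuation, Section 10.1 gives a fixed list of primary reasons: lack of efficacy, adverse event, withdrawal by subject, lost to follow-up, pregnancy, death, other. If adverse event or other is chosen, "a specification must be provided in the eCRF with a clear link to the specific AE if applicable". Section 14.3.1 presents the reasons by treatment group. Section 14.3.9.1 adds: "AEs leading to withdrawal from trial and AEs leading to permanent discontinuation of IMP will be tabulated by treatment group and listed".

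**The concern.** Two rules apply to the same event and give different answers. If a subject stops IMP because of non-serious burning, Section 11.4.5 says no AE is recorded, while Appendix 1 and Section 13.3 point to an AE record. A site is likely to follow the specific instruction over the general definition, but sites may differ.

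The choice decides which tables show the event. Number of AEs is the only safety endpoint in Panel 3, comparing the safety of each strength with vehicle is a stated objective, and Section 5.3 says the results will support phase 3 dose selection. Section 5.2 says the cream had not been tested in a clinical trial, so its local tolerability was unknown. A table of AEs leading to discontinuation that omits stops for local intolerance would be incomplete for that purpose.

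**Working it through.** The plan states no figure on this point, so the check is a side-by-side reading followed by an illustration of size.

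**Step 1: the conflict.** Take a subject with non-serious grade 3 burning who stops IMP for it.

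- Section 11.4.5: not serious, so not reported as an AE.
- Appendix 1: being an anticipated effect is no ground for exclusion. The reason for an unfavourable, unplanned medication change is an AE. Stopping IMP is not named there, but it plausibly falls under that wording.
- Section 13.3: a subject-reported AE goes on the AE form, with duration, severity, causality, outcome and action taken with IMP (drug withdrawn is one of the choices).

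No text says which rule prevails.

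**Step 2: where the event appears if Section 11.4.5 is followed.**

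- AE count and AE tables (Section 14.3.9.1): absent.
- AEs leading to permanent discontinuation of IMP (Section 14.3.9.1): absent, because the table holds only recorded AEs.
- Local tolerability summary (Section 14.3.9.4): present as a grade, without action taken or outcome. Section 14.3.12 uses observed cases for tabulations by visit, so a subject who has stopped and no longer attends leaves the later denominators. No table of worst grade at any visit is planned.
- Disposition (Section 14.3.1): present as a reason for stopping, but the list has no tolerability option. There are three plausible codings:
  - *Adverse event*: a specification is required, but there is no AE to link to. Disposition would count the stop while the AE discontinuation table would not.
  - *Other*: a specification is required, but the subject is counted under other.
  - *Withdrawal by subject*: no specification is required.

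No output described in the documents joins the grade to the stop.

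**Step 3: size.** Input from the documents: 50 subjects per arm (Section 14.1). The rate *p* of stopping IMP for non-serious stinging/burning is an assumption. Expected number missing per arm = 50 × *p*; chance of at least one = 1 − (1 − *p*)^50.

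| Assumed *p* | Expected per arm | Chance of at least one |
|---|---|---|
| 2% | 50 × 0.02 = 1 | 1 − 0.98^50 = 64% |
| 5% | 50 × 0.05 = 2.5 | 1 − 0.95^50 = 92% |
| 10% | 50 × 0.10 = 5 | 1 − 0.90^50 = 99.5% |

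An arm with 2 such stops, for example, would show 0/50 (0%) for this cause in the AE discontinuation table instead of 2/50 (4%).

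**The case against.** The strongest reply is that separate reporting is deliberate and the data are collected well. Amendment 1 added the scale so that local tolerability would be actively assessed. Section 13.2 collects AEs by a non-leading question, so there is a case for keeping a solicited symptom out of the AE counts. The scale is scheduled on Day 4, at Weeks 1, 2, 4, 6 and 8, and at unscheduled visits. A subject who stops early is asked to attend an early termination visit with the Week 8 procedures, so a grade is due close to the stop. The grade is defined in connection with IMP applications, so the lack of a causality field matters less than it might.

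All of that stands, and it rules out several stronger readings:

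- A reader might infer that stinging/burning can never be an AE unless serious, even when it ends treatment. Section 11.4.5 does not mention discontinuation, and Appendix 1 points the other way. The documents contradict each other; they do not settle the matter.
- A reader might infer that this is the cream's most likely dose-related harm. Nothing supports that: the cream had no prior clinical trial, and Section 5.2 reports no apparent dose-dependent AE trend with the ointment.
- A reader might infer that Section 10.1 always demands a linked AE, leaving the stop unrecordable. The link is asked for only where applicable, and other can be used with a specification.
- A reader might infer that the trial hides the harm. Grades and reasons for stopping are both tabulated by arm.

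The reply does not remove the conflict between the recording rules, and it does not supply an output that shows how many subjects in each arm stopped because of local intolerance.

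**Conclusion.** The point holds as a contradiction in the recording rules with a limited reporting consequence. Followed literally, Section 11.4.5 removes non-serious local reactions that led to stopping IMP from the AE count and from the AE-leading-to-discontinuation table. The remaining outputs show grade and reason for stopping separately and do not link them.

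The size is unknown. The figure of 1 to 5 of 50 subjects per arm rests wholly on assumed rates of 2% to 10%, and on sites following 11.4.5 over Appendix 1. If no subject stops for stinging or burning, the discontinuation table is unaffected. The dose-response analysis of efficacy is not in question. A correction is worth making because it is cheap and changes what the safety tables show.

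**What to change.** Reconcile Section 11.4.5 with Appendix 1 and Section 13.3. Keep the 4-point scale. State in 11.4.5 that a local tolerability reaction is also recorded as an AE when it leads to permanent discontinuation of IMP, to withdrawal from the trial or to treatment of the reaction, as well as when it is serious.

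Add to Section 14.3.9.4 a by-arm table of the worst grade at any visit, including early termination and unscheduled visits, and of the number of subjects whose IMP discontinuation was attributed to local tolerability. Specify it before the randomisation code is broken.

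This governs recording and reporting only and sets no rule on when IMP is stopped. The cost is one sentence, a notice to sites and one extra table. The downside is that a few reactions will be recorded both on the scale and as AEs.
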